### 10.3 Sample Size Considerations

In Dose Escalation, this study will utilize the BLRM (Neuenschwander et al. 2008) and following the escalation with overdose control (EWOC) principle (Babb et al. 1998, Rogatko et al. 2005) to guide dose finding with at least 3 DLT-evaluable patients per dose level. The number of patients enrolled will depend on actual data. The average sample size is 18 based on the simulation with the assumption of 8.0% and 24.5% at 1.6 mg/kg and at 9.6 mg/kg, respectively, with 9.6 mg/kg as the highest dose tested. In addition, to refine the RDE, additional patients may be enrolled into selected dose levels.

In Dose Expansion, up to approximately 30 patients will be enrolled in each cohort. The sample size is determined such that sufficient precision is achieved to exclude a clinically non-interesting ORR associated with the current standards of care. The exact 95% and 90% confidence intervals at various ORR are provided in Table 3. Assuming the ORR is approximately 20% in current standard of care (Deciphera 2019, Heinrich et al. 2018, Heinrich et al. 2019), the efficacy of DS-6157a over the standard of care can be concluded if observed ORR in the cohort is greater than or equal to 36.7%.

**Table 3 Exact CI for sample size of 30 at various observed ORR**

Sample size	Observed ORR	Exact 95% CI	Exact 90% CI
N=30	30.0%	[14.7, 49.4]	[16.6, 46.5]
	33.3%	[17.3, 52.8]	[19.3, 49.9]
	36.7%	[19.9, 56.1]	[22.1, 53.3]
	40.0%	[22.7, 59.4]	[25.0, 56.6]
	43.3%	[25.5, 62.6]	[27.9, 59.8]
	46.7%	[28.3, 65.7]	[30.8, 63.0]
	50.0%	[31.3, 68.7]	[33.9, 66.1]

The confidence intervals are calculated based on the binomial distribution using Clopper-Pearson method using SAS® version 9.4.

CONFIDENTIAL

If multiple doses or regimens are selected in one or more cohorts for Dose Expansion (Part 2), then up to approximately 30 patients may be randomized into each dose or regimen in one or more cohorts. Intra-patient dose escalation (IPDE) may be allowed for selected patients (Section 6).

#### 10.4 Analysis Populations

The following analysis populations will be used:

- **Safety Analysis Set** will include all patients who received any DS-6157a. For this study, the Full Analysis Set and the Safety Analysis Set are identical for patients enrolled in the nonrandomized portion of the study.

Patient data will be analyzed according to the study treatment received, where treatment received is the randomized/assigned study drug treatment if the patient took at least one dose of the randomized/assigned study drug treatment; otherwise the first treatment received will be used.

- **DLT-Evaluable Set** will include all patients enrolled in Dose Escalation (Part 1) of the study who had a DLT, or who received the full dose of DS-6157a in Cycle 1 and completed the DLT evaluation period.
- **Full Analysis Set (FAS)** will include all patients who received any DS-6157a.
- **PK Analysis Set** will include all patients in safety analysis set who had at least one PK sample with measurable concentration.

Demographic and baseline characteristics, disposition, and safety analyses will be presented for the Safety Analysis Set. In addition, for randomized patients, disposition will also be presented for FAS. Efficacy analyses will be presented for FAS. Analysis of PK parameters will be based on the PK analysis set.

Efficacy and safety endpoints observed after IPDE will be summarized separately from the rest of the results; these summaries may include tables, listings, or figures as appropriated depending on the number of patients and amount of data observed post-IPDE. Further details on this will be given in the SAP.

#### 10.5 Data Analysis

##### 10.5.1 Study Population Data

Disposition and reasons for discontinuing the study treatment and discontinuing from the study will be summarized and listed for the FAS and Safety Analysis Set. Demographic and baseline characteristics such as age, sex, race, ethnicity, baseline ECOG performance status, histology, cancer stage, best response to prior chemotherapy, lines of prior regimens, and prior treatment type will be summarized for the Safety Analysis Set.

*CONFIDENTIAL*

### 10.5.2 Efficacy Analysis

Efficacy analyses will be based on FAS. If multiple doses or regimens were selected for Dose Expansion (Part 2) and not all randomized patients receive at least one dose of DS-6157a dose/regimen as randomized, sensitivity analyses will be performed for the Safety Analysis Set.

Efficacy variables will include BOR, ORR, DCR, CBR, DoR, TTR, and PFS using RECIST Version 1.1. In this study, best response determination using RECIST Version 1.1 requires confirmation of CR or PR.

A brief description of each endpoint is provided below.

- The BOR will be determined using tumor assessments performed before the start of any follow-up anticancer therapies (i.e. anticancer drug, radiotherapy, or surgery).
  - CR = at least two determinations of CR at least 4 weeks apart before progression.
  - PR = at least two determinations of PR or better at least 4 weeks apart before progression (and not qualifying for a CR).
  - SD = at least one SD assessment (or better) >6 weeks after randomization/starting treatment and before progression (and not qualifying for CR or PR).
  - PD = progression  $\leq$ 12 weeks from randomization/start of study treatment (and not qualifying for CR, PR, or SD).
  - NE = all other cases
- ORR is defined as the proportion of patients with BOR of CR or PR.
- DCR is defined as the proportion of patients with BOR of CR, PR, or SD.
- CBR is defined as the proportion of patients with BOR of CR or PR, or patients with SD lasting at least 180 days.
- DoR is defined as the duration from the first documented response to the date of progression or death due to any cause. In case a patient does not have progression or death, DoR is censored at the date of last adequate tumor assessment (defined as an assessment of CR, PR, or SD). DoR analysis will include only responders.
- TTR is defined as the time from randomization/start of study treatment to the date of first documented response. TTR analysis will include only responders.
- PFS is defined as the time from randomization/start of study treatment to the date of event defined as the first documented radiological progression or death due to any cause. If a patient has not had an event, PFS is censored at the date of last adequate tumor assessment.

The efficacy variables will be listed and summarized. Objective response rate, DCR, and CBR will be summarized with the 90% and 95% confidence intervals using the Clopper-Pearson method. For DoR and PFS, the survival distribution of these endpoints will be summarized and presented graphically using the Kaplan-Meier method, and median event times and their 2-sided 95% CI using Brookmeyer and Crowley methods will be presented. Time to response will be summarized descriptively.

*CONFIDENTIAL*

Descriptive statistics for the best percentage change from baseline in the sum of dimensions (SoD) of measurable tumors will be provided. A waterfall plot of the best percent change in the SoD for each patient will be presented.

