### **10.2 General Statistical Considerations**

The data cut-off for the primary analysis will occur after all patients have either discontinued the study or have been followed for at least 6 months, whichever is earlier.

Data will be summarized by cohort and dose level, and overall when appropriate.

Descriptive statistics on continuous data will include mean, median, standard deviation, and range (as well as geometric mean and geometric coefficient of variation for PK data), while

*CONFIDENTIAL*

categorical data will be summarized using frequency counts and percentages. Graphical summaries of the data may be presented. Time to events endpoints will be reported using Kaplan-Meier estimates.

No statistical testing is planned for this study. If multiple doses or regimens are selected for Dose Expansion (Part 2), then no statistical comparison among the doses or regimens is planned.

Assessments of change from baseline to post-treatment or the ratio of post-treatment to baseline will include only those patients with both baseline and post-treatment measurements. The last non-missing value of a variable taken before the first dose of study drug will be used as the baseline value, unless otherwise specified. In general, missing data will not be imputed for the purpose of data analysis, unless otherwise specified.

A detailed statistical analysis plan (SAP) describing the methodology to be used in analysis will be prepared and finalized before database lock. Statistical methods described within this document may be changed based on advances in research.

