## 10.6 Statistical Analysis Process

The clinical study will be analyzed by Sarah Cannon Development Innovations according to this protocol and the SAP, which will detail all methodologies and displays/shells for statistical analyses.

The SAP will provide the statistical methods and definitions for the statistical analysis of the efficacy, safety, PK and other data, as well as describe the approaches to be taken for summarizing other clinical study information such as patient disposition, demographic and baseline characteristics, study drug exposure, and prior and concomitant medications. The SAP will also include a description of how missing, unused, and spurious data will be addressed. The pharmacokinetic modeling of the concentration data, and the exposure/response analysis will be outside the scope of the SAP.

To preserve the integrity of the statistical analysis and clinical study conclusions, the SAP will be finalized prior to database lock for primary analysis.

All statistical analyses will be performed using SAS® Version 9.3 or higher (SAS Institute, Cary, NC 27513), unless specified otherwise in this protocol or in the SAP. The BLRM will be implemented using East® (Versions 6.5, Cytel, Inc.) with the BLRM module.

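### If Part 2 is randomised, the Section 10.5.2 sensitivity analysis covers the same patients as the primary efficacy analysis and cannot reflect patients randomised but never dosed

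*Combined protocol and SAP*

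**What the plan says.** Section 10.4 says that the Safety Analysis Set "will include all patients who received any DS-6157a" and defines the FAS by the same words. It has no separate FAS rule for randomised patients.

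Other wording in Section 10.4 treats the two sets as different once patients are randomised. It says that the "Full Analysis Set and the Safety Analysis Set are identical for patients enrolled in the nonrandomized portion of the study", and that "for randomized patients, disposition will also be presented for FAS".

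A paragraph printed under the Safety Analysis Set assigns patients to their randomised treatment if they took it at least once; "otherwise the first treatment received will be used". No grouping rule is stated for the FAS by name.

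Section 10.5.2 bases efficacy on the FAS. For a Part 2 with several doses or regimens it adds that, if "not all randomized patients receive at least one dose of DS-6157a dose/regimen as randomized, sensitivity analyses will be performed for the Safety Analysis Set".

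Section 10.3 allows efficacy over standard of care (assumed ORR about 20%) to be concluded at an observed ORR of 36.7% or more, with N = 30. Section 10.2 says that with multiple doses or regimens "then no statistical comparison among the doses or regimens is planned".

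**The concern.** A sensitivity analysis is informative when it changes something that the primary analysis holds fixed. The trigger in Section 10.5.2 is met in two situations: a randomised patient took only some other dose level, or a randomised patient took nothing. A Safety Analysis Set analysis may be able to deal with the first. It cannot deal with the second, because such a patient is in neither set.

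The per-cohort ORR carries a stated conclusion against standard of care, so its denominator matters. A report could show a prespecified check agreeing with the primary result when agreement was guaranteed. Two analysts could also group the FAS differently, because its grouping rule is not explicit.

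**Working it through.** **Membership.** Apply the two Section 10.4 definitions to a constructed case: 60 randomised, 30 to A and 30 to B. In A, 2 are never dosed and 1 receives only B.

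- FAS: 60 − 2 = 58. Safety Analysis Set: 60 − 2 = 58. The members are the same.
- Grouped as randomised: A 28, B 30. Grouped as received: A 27, B 31.
- If the as-received paragraph applies to all analyses, both use 27/31 and are identical.
- If the FAS is grouped as randomised, the one patient who took only B is the sole source of difference.
- The 2 never-dosed patients are absent on either reading.

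**Reproducing the plan's figure.** The Clopper-Pearson 90% lower limit is the 5th percentile of Beta(x, n − x + 1), and the upper limit is the 95th percentile of Beta(x + 1, n − x). For 11/30 this gives 22.1% to 53.3%, as in Table 3. All seven rows of Table 3 reproduce at 90% and 95%.

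**Size.** The documents give no never-dosed count, so I assume k = 0 to 3 of 30, with n = 30 − k dosed. The threshold can be carried to smaller n in two ways.

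1. *Literal: observed ORR of at least 11/30.* The minimum number of responders is 11n/30 rounded up: 10.6 → 11 at n = 29, 10.3 → 11 at n = 28, 9.9 → 10 at n = 27.
2. *Lower bound: exact 90% lower limit above 20%.* This is the reasoning by which Section 10.3 and the synopsis arrive at 36.7%. Ten responders give the limits in the table. Nine are never enough (for example, 9/27 gives 18.6%).

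The probability of passing is the binomial probability of at least the minimum number of responders among n, at a true ORR of 20%.

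| Dosed n | 10/n | 90% lower limit for 10/n | Minimum, literal | Pass probability | Minimum, lower bound | Pass probability |
|---|---|---|---|---|---|---|
| 30 | 33.3% | 19.33% | 11 | 2.6% | 11 | 2.6% |
| 29 | 34.5% | 20.05% | 11 | 2.0% | 10 | 4.9% |
| 28 | 35.7% | 20.82% | 11 | 1.5% | 10 | 3.9% |
| 27 | 37.0% | 21.66% | 10 | 3.0% | 10 | 3.0% |

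On the all-randomised denominator, 10/30 = 33.3% with lower limit 19.33% fails both versions, and 11/30 passes both. The dosed-only and all-randomised decisions therefore differ only at exactly 10 responders. Under the literal rule that requires k = 3. Under the lower-bound rule k = 1, 2 or 3 is enough.

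**The case against.** The strongest reply is that Section 10.5.2 was never meant to count never-dosed patients. Its trigger resembles the as-received rule in Section 10.4, so it can be read as a regrouping check for patients given another level. That is a fair reading of half the trigger, and the analysis may serve that half. The trigger's wording nevertheless also covers patients who received nothing. If the as-received paragraph is general, the check does not serve even the first half, because nothing is regrouped.

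A second reply is that an all-randomised analysis is a preference. The summary of changes shows that an FAS based on randomisation was removed, and deleting the leftover wording would also restore consistency. It would, but it would leave no analysis of incomplete dosing, which the current text evidently wants. This point rests on the current Sections 10.4 and 10.5.2, not on the removed text.

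A third reply is that the issue is conditional and the SAP may settle it. Randomisation is optional and the never-dosed count may be zero. Section 10.6 says that the SAP will "describe the approaches to be taken for summarizing other clinical study information such as patient disposition". A reader might infer that the number randomised and not dosed will go unreported; the documents do not support that, because disposition displays are left to the SAP. No all-randomised efficacy set is defined in the text reviewed.

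**Conclusion.** The point holds, conditional on a randomised Part 2. The prescribed sensitivity analysis repeats the primary population, and at most regroups patients who never took their randomised level. The Section 10.4 wording that presupposes different sets has no support in the current definitions.

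Three stronger readings do not follow:

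- *The dosed-only FAS is unsound as the primary set.* It is acceptable here, and under either version of the threshold the pass probability at a true ORR of 20% stays below 5% for 27 to 30 dosed.
- *A comparison between randomised doses is compromised.* None is planned.
- *The check has no possible use.* It can regroup patients if the FAS is analysed as randomised.

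Nor can one say without qualification that 1 or 2 never-dosed patients leave the decision unchanged. That is true of the literal 36.7% rule but not of the lower-bound criterion.

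The size rests on the assumed 0 to 3 never dosed of 30 and on the version of the threshold used. Severity is minor.

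**What to change.** Keep the dosed-only FAS as the primary efficacy set. For randomised cohorts, define the Section 10.5.2 sensitivity population as all randomised patients, analysed as randomised, with never-dosed patients counted as non-responders for ORR, disease control rate and clinical benefit rate. The best-response scheme already accommodates them through "NE = all other cases".

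State whether the FAS is grouped as randomised or as received. Align the Section 10.4 sentences on identity of the sets and on disposition with whatever definitions remain.

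The cost is a few sentences in Sections 10.4 and 10.5.2, or in the SAP before database lock, and one small extra analysis. The sensitivity ORR will be slightly lower if some patients are not dosed; the primary ORR is unaffected.

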Treatment day (d)	Within -28 to 0 days	1	2	4 ±1 d	8 ±1 d	15 ±1 d	22 ±2d h	1 +2d	8 ±2d	15 ±2d	22 ±2d h	1 ±2d	2	4 ±2d	8 ±2d	15 ±2d	22 ±2d h	1±2d				
HIV, HBV, HCV testing a	X a																					
Eye exam f	X																			X		
Tumor assessment g	X a	Every 6 weeks (±7 days) in the first 36 weeks from Day 1 of Cycle 1, and every 9 weeks (±7 days) thereafter.																X g		X r		
Blood sampling for pharmacokinetics h		X	X	X	X	X	(X) h	X	X	X	(X) h	X	X	X	X	X	(X) h	X h				
Blood sampling for anti-drug antibodies (ADAs) i		X			X			X				X						X i	X i	X i	(X) i	
COVID-19 sample		X																	X s	X		
Blood sampling for cfDNA analysis j	X j								DAY 8 TO 15 j										X j	X j		
Blood sampling for cfRNA analysis k	X k								DAY 8 TO 15 k										X k	X k		

CONFIDENTIAL

Study Drug: DS-6157a

Sponsor/Innovations Study Numbers: DS6157-A-U101/GI 289

Final Protocol: 17 August 2021 Version 6.0

Study period	Screening	Dose Escalation and Dose Expansion DS-6157a Monotherapy Treatment Period																	EOT p	30-day Safety FU q	Long-term FU r		
		C1						C2				C3						C4+				After EOT	After 30-day Safety FU
Treatment day (d)	Within -28 to 0 days	1	2	4 ±1 d	8 ±1 d	15 ±1 d	22 ±2d h	1 +2d	8 ±2d	15 ±2d	22 ±2d h	1 ±2d	2	4 ±2d	8 ±2d	15 ±2d	22 ±2d h	1±2d					
Archival tumor sample (optional) l	X																						
Fresh tumor sample m	X							DAY 8 TO 15														(X) m optional	
PBMC and serum biomarker collection n		X			X			X				X											
DS-6157a infusion o		X						X				X							X				
Concomitant medication/procedures	X	X	X	X	X	X		X	X	X		X	X	X	X	X		X	X	X			
Adverse events p	X	X	X	X	X	X		X	X	X		X	X	X	X	X		X	X	X			
Patient status																					X	X	
PK Sampling for CQ/HCQ administration		If chloroquine (CQ) or hydroxychloroquine (HCQ) is administered for COVID-19, additional PK blood samples should be collected at the following visits, if feasible: 
 
• Prior to the first CQ or HCQ dose (Day 1)
 
																					

CONFIDENTIAL

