- g Tumor assessments must be done according to Response Evaluation Criteria in Solid Tumors (RECIST) Version 1.1 (see [Appendix B](#)) and should include computed tomography (CT) scans or magnetic resonance imaging (MRI) of **the chest and abdominopelvic cavity** at screening and, if clinically indicated, imaging of any other known or suspected sites of disease (e.g., brain) using an appropriate method (CT scan or MRI). If there is a history or suspicion of CNS metastasis a CT scan of the head or MRI of the brain must be performed. The same radiographic procedure must be used throughout the study. In case of suspected (but not otherwise confirmed) bone metastasis at screening or in subsequent cycles, tumor assessment should include a bone scan. CT scans or MRI of **the abdominopelvic cavity** (and chest ONLY if the screening imaging documented sites of disease in the chest) and correlative imaging should then be repeated at each tumor assessment. Assessments will be performed by the Investigator at screening and every 6 weeks ( $\pm 7$  days) during the first 36 weeks, and then every 9 weeks ( $\pm 7$  days), taking as reference the first dose date for non-randomized patients and randomization date for randomized patients. Thereafter, patients will be evaluated at the EOT visit by CT scans or MRI of **the chest and abdominopelvic cavity**, and as clinically indicated, until PD as per RECIST Version 1.1 as assessed by the Investigator, initiation of new anti-cancer treatment, unacceptable toxicity, death, lost to follow up, or withdraw of consent from any further participation and at the discretion of the Investigator. Baseline tumor assessments must be performed within 28 days before first administration of study drug for non-randomized patients and must be before randomization date for randomized patients. Tumor assessments should occur regardless of dose interruptions/delays. Additionally, all images including CT and MRI may be submitted to a central imaging vendor for independent retrospective review (Section 7.3).

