## 2.4 Endpoints

**Table 1 Study Objectives and Corresponding Endpoints**

Primary Objectives:	Endpoint/Variable:

 
• Dose Escalation: To investigate the safety and tolerability and to determine MTD and RDE of DS-6157a
 
• Dose Expansion: To investigate the safety, tolerability, and efficacy of DS-6157a at RDE
 
	Dose-limiting toxicities (DLTs) Serious adverse events (SAEs) Treatment-emergent adverse events (TEAEs) Adverse event (AE) of special interest (AESIs) Chemistry/hematology laboratory parameters Physical examination Vital signs Electrocardiograms (ECGs) LVEF by echocardiogram (ECHO)/multi-gated acquisition scan (MUGA) Ophthalmologic findings Dose Expansion only: Objective response rate (ORR), duration of response (DoR), disease control rate (DCR), clinical benefit rate (CBR), time to response (TTR), progression-free survival (PFS), and best percent change in target lesion by RECIST Version 1.1

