### 7.3 Tumor Assessments During Study Treatment

Patient will remain on treatment as long as, in the opinion of the Investigator, they are deriving benefit and the criteria for withdrawal listed in Section 3.3 are not met. Please refer to the [Assessment Schedule](#) for detailed outlines of each visit during the treatment period for each part of the study.

Response will be assessed by CT scans or MRI of **the abdominopelvic cavity** (and chest ONLY if the screening imaging documented sites of disease in the chest) at 6-week intervals ( $\pm 7$  days) during the first 36 weeks and every 9 weeks ( $\pm 7$  days) thereafter, taking as reference the first dose date for non-randomized patients and the randomization date for randomized patients. Then, patients will be assessed at the EOT visit by CT scans or MRI of **the chest and**

*CONFIDENTIAL*

**abdominopelvic cavity**, and at the discretion of the Investigator. Patients will continue treatment with DS-6157a, until progression of disease (PD) according to RECIST Version 1.1 as assessed by the Investigator, initiation of new anti-cancer treatment, unacceptable toxicity, death, lost to follow up, or withdrawal of consent. However, patients may be treated beyond initial radiological progression (according to RECIST Version 1.1) on a case-by-case basis (with agreement from the Medical Monitor), if the Investigator feels that it is in the patient's best interest, the patient re-consents to continue receiving study treatment in a separate consent form, and as long as the patient is deriving benefit from the treatment, and no other criterion listed in Section 3.3 is fulfilled.

The assessments to be performed at this time are specified in [Appendix B](#) and will occur regardless of dose interruptions/delays. Please refer to Section 9 for further instructions on evaluating response (e.g., PD, SD).

The following assessments will be performed if abnormal at baseline or if clinically indicated:

- CT scan or MRI of the chest, abdomen, and pelvis/lower abdomen
- CT scan of the head/MRI of the brain if history of CNS metastasis
- Bone scan in case of suspected (but not confirmed) bone metastasis

Additionally, all images including CT and MRI may be submitted to a central imaging vendor for independent retrospective review.

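### The stable-disease minimum of more than 6 weeks excludes about half of the permitted first-scan window, so BOR and DCR can turn on the appointment day

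*Combined protocol and SAP*

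**What the plan says.** Section 10.5.2 builds best overall response (BOR) as a hierarchy. The stable-disease level reads "SD = at least one SD assessment (or better) >6 weeks after randomization/starting treatment and before progression", for patients who do not qualify for CR or PR. Progression within 12 weeks is PD if none of the better categories applies, and every remaining case is NE. Section 10.5.2 then states: "DCR is defined as the proportion of patients with BOR of CR, PR, or SD".

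The Assessment Schedule sets tumour assessments at "Every 6 weeks (±7 days) in the first 36 weeks from Day 1 of Cycle 1". Footnote g fixes the origin, "taking as reference the first dose date for non-randomized patients and randomization date for randomized patients", and section 7.3 does the same: "taking as reference the first dose date for non-randomized patients and the randomization date for randomized patients". This is also the origin that the SD rule uses.

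Table 1 lists "disease control rate (DCR), clinical benefit rate (CBR") among the Dose Expansion endpoints under the primary objectives. Section 10.5.2 gives the reporting: "Objective response rate, DCR, and CBR will be summarized with the 90% and 95% confidence intervals using the Clopper-Pearson method".

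Appendix B defines SD at a single time point and sets no minimum interval. Its special notes contain no rule on visit windows.

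**The concern.** The scan schedule tolerates a week either side of the due date, while the SD rule has a hard lower limit at the due date itself. A site that scans a few days early, within its permitted window, produces an assessment that cannot support SD. If the next scan shows progression, or there is no next scan, that patient is lost to DCR. A patient with the same findings who is scanned a few days late is counted.

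The rule accepts an assessment of SD or better, so the same cut-off applies to an unconfirmed CR or PR at an early first scan that is followed by progression. That patient cannot fall back to SD either.

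The day count is also undefined. Whether a scan exactly on the due date qualifies depends on whether the reference date is day 0 or day 1, so two programmers working from section 10.5.2 could classify the same on-time scan differently.

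At stake is whether DCR describes tumour behaviour or partly describes scheduling. If several doses are expanded side by side, scan timing would add noise to the comparison of their DCRs.

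**Working it through.** **Inputs**

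- First scan: 6 weeks ±7 days (Assessment Schedule), from first dose, or from randomization if randomized (footnote g; section 7.3).
- SD minimum: more than 6 weeks, i.e. more than 42 days, from the same date (section 10.5.2).
- PD limit: 12 weeks, i.e. 84 days; everything else NE (section 10.5.2).
- Cohort size for illustration: 30 (section 10.3).
- Interval method: Clopper-Pearson (section 10.5.2).

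**Step 1. The window.** 42 − 7 = 35 and 42 + 7 = 49, so the permitted days number 49 − 35 + 1 = 15.

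**Step 2. Which days can support SD.** Let d be the elapsed days from the reference date to the scan.

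| Day count | Condition | Days that fail | Days that pass |
|---|---|---|---|
| Elapsed days | d > 42 | 35–42 (8 of 15) | 43–49 (7 of 15) |
| Reference date = day 1 | d + 1 > 42 | 35–41 (7 of 15) | 42–49 (8 of 15) |

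On the elapsed-day count the due date, day 42, fails. On the other count it passes.

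**Step 3. Resulting BOR when the first scan is the only non-PD scan** (elapsed-day count). The second scan is due at 84 ± 7, i.e. days 77–91.

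| What follows the first scan | First scan on days 35–42 | First scan on days 43–49 |
|---|---|---|
| PD on days 77–84 | PD | SD |
| PD on days 85–91 | NE | SD |
| No later scan | NE | SD |

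The middle row gives NE for a patient with two readable, on-schedule scans, because the PD category stops at day 84 while the second-scan window runs to day 91.

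A non-PD scan at the second visit falls on day 77 at the earliest. It exceeds 42 days whatever the first-scan day, so only patients without such a scan are affected.

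**Step 4. Size.** One patient in 30 is 1/30 = 3.3 percentage points of DCR. For x of n, the Clopper-Pearson limits at level 1 − α are the α/2 quantile of Beta(x, n − x + 1) and the 1 − α/2 quantile of Beta(x + 1, n − x). All seven rows of Table 3 ("Exact CI for sample size of 30 at various observed ORR") reproduce exactly; for instance, 11/30 = 36.7% gives 95% CI 19.9–56.1 and 90% CI 22.1–53.3.

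Table 3 is built for ORR, but DCR uses the same method, so at the same N its adjacent rows show what one patient does. For an arbitrary adjacent pair:

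| x/30 | Rate | 95% CI | 90% CI |
|---|---|---|---|
| 14 | 46.7% | 28.3–65.7 | 30.8–63.0 |
| 15 | 50.0% | 31.3–68.7 | 33.9–66.1 |

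The lower 90% bound moves by 33.9 − 30.8 = 3.1 points and the lower 95% bound by 31.3 − 28.3 = 3.0 points.

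**Step 5. Check of the proposed rule.** With d ≥ 35, all 15 permitted days pass, and every cell in the table of step 3 becomes SD.

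**The case against.** Five points can be made for leaving the text alone.

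- **The SAP may settle it.** Section 10.5.2 presents its definitions as short descriptions, and section 10.6 assigns definitions to a SAP finalized before database lock. This holds for the day-count convention. It does not hold for the limit itself: more than 6 weeks is a stated rule, and a SAP would have to change it, not complete it. No SAP text available here does so.
- **Strictness may be deliberate.** A scan on day 36 documents less disease control than one on day 48, and Appendix B imposes no minimum that is being broken. A strict minimum is a legitimate choice. One that accepts or rejects compliant first scans by appointment day, and on one reading rejects the due date, is hard to see as intended.
- **No decision rests on it.** Cohort 2 opens on objective responses or SD of at least 6 months (Figure 1 footnote). An optional Cohort 3 depends on an objective response (section 5.1.4). The 36.7% criterion is for ORR (section 10.3). RDE selection has no DCR threshold, no formal interim analysis is planned (section 10.8.3), and no testing is planned (section 10.2). DCR is one of seven efficacy endpoints in its row of Table 1. All of this stands and limits the weight of the point.
- **The size is illustrative.** Seven or eight of 15 counts calendar days, not patients. The documents give neither the distribution of scan days nor the number of patients with this course. This stands.
- **The change favours the drug and is incomplete for BOR.** DCR can only stay the same or rise. The separate mismatch between the 84-day PD limit and the second-scan window to day 91 also remains: a patient with a missed first scan and PD on days 85–91 is still NE. Both are true; the second does not affect DCR.

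**Conclusion.** The concern holds. As written, section 10.5.2 and the scan schedule do not fit together, and nothing else in the documents reconciles them. For a patient whose only non-PD scan is the first, BOR switches between SD and PD or NE, and the patient moves into or out of DCR, according to the day chosen within the permitted window. Between 7 and 8 of the 15 permitted days fail, depending on an unstated day count. Each affected patient is worth 3.3 points of DCR in a cohort of 30; the number of such patients is unknown.

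ORR and PFS are unaffected, as is CBR when scans are on schedule, since its SD must last at least 180 days. Patients with a non-PD scan at week 12 or later are also unaffected. This is a cheap improvement to a descriptive endpoint and does not threaten the trial's conclusions. The result assumes that scans stay within the ±7-day window and that the rule is applied literally.

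**What to change.** In section 10.5.2, and identically in the SAP, replace the SD line with wording to this effect:

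> Stable disease: at least one assessment of SD or better made 35 days or more (6 weeks less the 7-day window) after the reference date and before progression, in a patient not qualifying for CR or PR. Days are counted as assessment date minus reference date.

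Every in-window first scan then counts alike, and the day count is settled. Scans earlier than day 35 still do not support SD.

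The change costs one line in each document, with no effect on visits, data collection or timing. Its price is a more lenient minimum (35 days instead of more than 42), so DCR can only stay the same or rise; the sponsor should say so when making the change. It should be made before database lock, so that it is not a choice taken with the DCR in view. If the sponsor prefers to keep the strict limit, the day count still needs stating, and the dependence on scan day should be acknowledged wherever DCR is reported.
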